 - b. Has previously demonstrated an inadequate response to or failed to tolerate corticosteroids or immunomodulators (ie, 6-MP, AZA, and MTX) but not a biologic, ie, the Bio-NF population (Appendix 3 of the Master protocol PLATFORMPACRD2001, Definitions of Inadequate Response to or Intolerance of Corticosteroids or AZA/6 MP and Corticosteroid Dependence)
9. Therapy for the treatment of Crohn's disease must include at least 1 of the following medications, which should have been maintained at stable doses prior to the baseline (Week 0) visit:
 - a. Oral 5-aminosalicylic acid (5-ASA) compounds
 - b. Oral corticosteroids at a prednisone-equivalent dose ≤ 25 mg/day, or 9 mg/day of budesonide, or 5 mg/day beclomethasone dipropionate
 - c. Antibiotics being used as a primary treatment of Crohn's disease
 - d. Conventional immunomodulators (ie, AZA, 6-MP, or MTX) if participants have been taking them for at least 12 weeks and have been at a stable dose for at least 4 weeks prior to baseline

Laboratory Parameters

10. Have screening laboratory test results within the following parameters:
 - a. Hemoglobin ≥ 8.0 g/dL

- b. White blood cell count (WBCs) $\geq 3.0 \times 10^3/\mu\text{L}$
- c. Neutrophils $\geq 1.5 \times 10^3/\mu\text{L}$
- d. Platelets $\geq 100 \times 10^3/\mu\text{L}$
- e. Serum creatinine $< 1.7 \text{ mg/dL}$
- f. Alanine aminotransferase (ALT) and aspartate aminotransferase (AST) concentrations must be within 2 times the upper limit of the normal range for the laboratory conducting the test
- g. Direct (conjugated) bilirubin $< 1.0 \text{ mg/dL}$

Pregnancy Testing

- 11. A woman of childbearing potential must have a negative highly sensitive serum (β -human chorionic gonadotropin [β -hCG]) pregnancy test result at screening and a negative urine pregnancy test result at Week 0.

Other

- 12. Must sign an informed consent form (ICF) indicating that he or she understands the purpose of, and procedures required for, the study and is willing to participate in the study
- 13. Must sign a separate ICF if he or she agrees to provide optional DNA samples for research (where local regulations permit). Refusal to give consent for the optional DNA research samples does not exclude a participant from participation in the study
- 14. Willing and able to adhere to the lifestyle restrictions specified in this protocol

JNJ-67864238 intervention cohort specific inclusion criteria start with the letter A and are listed below.

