10.4. Appendix 4: Liver Safety: Suggested Actions and Follow-up Assessments

10.4.1. Stopping Algorithm

Study intervention will be discontinued for a participant if liver chemistry stopping criteria are met.

Phase 2 Liver Chemistry Stopping Criteria and Increased Monitoring Algorithm (no preexisting liver disease)

Abbreviations: ALT = alanine transaminase; AST = aspartate transaminase; INR = international normalized ratio; SAE = serious adverse event; ULN = upper limit of normal; Tbili = total bilirubin

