10.4.2. Follow-up Assessments

Phase 2 liver chemistry stopping criteria are designed to assure participant safety and to evaluate liver event etiology.

Liver Chemistry Stopping Criteria	
ALT/AST--absolute	ALT or AST- \geq5xULN
ALT/AST- Increase	If cannot monitor: ALT or AST- \geq 3xULN and cannot be monitored weekly for 4 weeks Or if able to monitor: ALT or AST- \geq 3xULN persists for \geq 4 weeks
Total bilirubin^{1, 2}	ALT or AST- \geq3xULN and total bilirubin \geq2xULN (or at least a doubling of direct bilirubin in known Gilbert's syndrome)
INR²	ALT or AST- \geq3xULN and international normalized ratio (INR) $>$1.5, if INR measured
Symptomatic³	ALT or AST- \geq3xULN associated with symptoms (new or worsening) believed to be related to liver injury or hypersensitivity

Suggested Actions, Monitoring and Follow-up Assessments

Actions	Follow-up Assessments

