## 5.6.3. Additional Safety Assessments

### 5.6.3.1. Clinical Laboratory Tests

Clinical laboratory tests will be displayed for the participants included in the safety analysis set. Clinical laboratory values are to be graded using National Cancer Institute Common Terminology Criteria for Adverse Events (NCI-CTCAE) version 5.0 (see [Table 3](#)). Descriptive statistics and graphical displays will be presented for chemistry and hematology at scheduled time points.

Change/percent change from baseline to time point will be summarized for chemistry, hematology, tests and displayed by intervention group.

- Summary of the observed values and changes from baseline over time through the final efficacy & safety visit for clinical laboratory parameters.
- Summary of maximum NCI-CTCAE toxicity grade for postbaseline laboratory values through Week 12 and through the final efficacy & safety visit for clinical laboratory parameters listed in [Table](#) . For toxicity grades, treatment emergent (TE) will be concluded if the postbaseline value is worse than the baseline value.
- Shift tables for selected clinical laboratory parameters (ALT, AST, alkaline phosphatase and total bilirubin) at Week 12.
- For abnormalities based on normal range and/or criteria: If the postbaseline value is above the upper limit and the baseline value is below the upper limit (eg, Normal or Low), then the postbaseline abnormality will be considered TE. The same applies to the postbaseline value being below the lower limit with the baseline value being above the lower limit (eg, Normal or High).
- If the baseline value is missing, a postbaseline abnormality will always be considered as TE.

Listings of participants with any abnormal postbaseline laboratory values of CTCAE grade  $\geq 2$  will also be provided.

The laboratory data to be summarized are as follows:

- **Hematology assessments:** hematocrit, hemoglobin, platelet count, total leukocytes and differential WBC count (neutrophils, lymphocytes, monocytes, eosinophils, and basophils)
- **Blood chemistry assessments:** ALT, AST, alkaline phosphatase, albumin, total and direct bilirubin, blood urea nitrogen, calcium, chloride, creatinine, phosphate, potassium, total protein, and sodium.

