The baseline value for a participant is the value closest to but prior to the first dose of study agent (Week 0). Change from baseline is defined to be the assessment at the postbaseline visit minus the assessment at baseline. Summaries of laboratory data will be completed using all the available laboratory data at the time point of interest without imputing missing data. Shift tables summarize the number of participants with low, normal, and high values (determined by the laboratory normal ranges) at the post baseline visit for each of the classifications of low, normal, and high at baseline.

Table 3: Grading Criteria for Clinical Laboratory Tests [CTCAE Version 5.0]

Table 3: Grading Criteria for Clinical Laboratory Tests [CTCAE Version 5.0]					
Hematology Tests		Criteria			
Test	Direction	1	2	3	4
Hemoglobin (g/dL)	Increase	>0 - 2	>2 - 4	>4	
Hemoglobin (g/dL)	Decrease	<LLN - 10.0	<10.0 - 8.0	<8.0	
Lymphocytes (/mm  )	Increase		>4000 - 20,000	>20,000	
Lymphocytes (/mm  )	Decrease	<LLN - 800	<800 - 500	<500 - 200	<200
Neutrophils (/mm  )	Decrease	<LLN - 1500	<1500 - 1000	<1000 - 500	<500
Platelets (/mm  )	Decrease	<LLN - 75,000	<75,000 - 50,000	<50,000 - 25,000	<25,000
Total WBC count (/mm  )	Increase			>100,000	
Total WBC count (/mm  )	Decrease	<LLN - 3000	<3000 - 2000	<2000 - 1000	<1000
Chemistry Tests		Criteria			
Test	Direction	1	2	3	4
ALT	Increase	>ULN - 3.0 x ULN if baseline was normal; 1.5 - 3.0 x baseline if baseline was abnormal	>3.0 - 5.0 x ULN if baseline was normal; >3.0 - 5.0 x baseline if baseline was abnormal	>5.0 - 20.0 x ULN if baseline was normal; >5.0 - 20.0 x baseline if baseline was abnormal	>20.0 x ULN if baseline was normal; >20.0 x baseline if baseline was abnormal
AST	Increase	>ULN - 3.0 x ULN if baseline was normal; 1.5 - 3.0 x baseline if baseline was abnormal	>3.0 - 5.0 x ULN if baseline was normal; >3.0 - 5.0 x baseline if baseline was abnormal	>5.0 - 20.0 x ULN if baseline was normal; >5.0 - 20.0 x baseline if baseline was abnormal	>20.0 x ULN if baseline was normal; >20.0 x baseline if baseline was abnormal
Albumin (g/L)	Decrease	≥30 - <LLN	≥20 - <30	<20	

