## **6.10. Appendix 10 Laboratory Toxicity Grading**

Laboratory Toxicity Grading related analysis will be performed as needed.

The grading scale use for lab assessments is based on ‘Common Terminology Criteria for Adverse Events (CTCAE) v5.0’.

If a laboratory value falls within the grading as specified below but also within the local laboratory normal limits, the value is considered to be normal and will be reset to grade 0.

Pre-baseline measurements will use the same grading ranges as applied to baseline measurements. In case a test has two sets of ranges – one for baseline normal and one for baseline abnormal, the one for baseline normal will be applied for all measurements taken pre-baseline and on baseline.

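### ALT/AST grading relative to an abnormal baseline lets a value that meets the protocol's 5xULN liver stopping criterion appear as Grade 1 and stay out of the Grade 2-or-higher laboratory listing

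*SAP*

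**What the plan says.** **Entry.** Protocol 5.1, criterion 10f, requires that ALT and AST "concentrations must be within 2 times the upper limit of the normal range for the laboratory conducting the test". A participant can therefore enter with a raised value. The Schedule of Activities (footnote r) lets Week 0 chemistry be omitted when screening tests are no more than 2 weeks old. SAP 5.6.3.1 takes the last value before first dosing as baseline, so a raised screening value can become the analysis baseline.

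**Grading after baseline.** SAP Table 3 has two scales for ALT and AST. With a normal baseline, Grade 2 is ">3.0 - 5.0 x ULN if baseline was normal". With an abnormal baseline, Grade 1 is "1.5 - 3.0 x baseline if baseline was abnormal" and Grade 2 is ">3.0 - 5.0 x baseline if baseline was abnormal".

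**Grading at baseline.** SAP 6.10 says that, for a test with two sets of ranges, "the one for baseline normal will be applied for all measurements taken pre-baseline and on baseline". A raised baseline is thus graded against ULN, and later values in the same participant against baseline.

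**Outputs.** SAP 5.6.3.1 plans a maximum-grade table, Week 12 low/normal/high shift tables, and "Listings of participants with any abnormal postbaseline laboratory values of CTCAE grade" 2 or higher.

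**Stopping criteria.** Protocol 10.4.1 states: "Study intervention will be discontinued for a participant if liver chemistry stopping criteria are met". The criteria in Protocol 10.4.2 include ALT or AST of at least 5xULN alone, and at least 3xULN combined with bilirubin, INR, symptoms, persistence or inability to monitor weekly. All are in ULN multiples, whatever the baseline.

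**The concern.** The protocol acts on one liver scale and the SAP's laboratory outputs report on another, and the two separate in the participants who start with raised enzymes. Two participants with the same peak ALT can receive different grades, and only one of them may reach the laboratory listing. The maximum-grade table then cannot be used to count, by arm, how many participants crossed the protocol's own liver thresholds.

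Safety is a secondary objective, and the protocol describes this as the first study of the compound in Crohn's disease. With 54 participants planned on active treatment, a single case is 1/54 = 1.9% of the arm, so one misplaced participant is visible in a table.

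**Working it through.** The SAP gives no figure to reproduce; this is a check of the grading rule.

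**Inputs.** Let b be baseline and x a post-baseline value, both in multiples of ULN. From Table 3, with an abnormal baseline (b > 1): Grade 1 if 1.5 ≤ x/b ≤ 3.0, Grade 2 if 3.0 < x/b ≤ 5.0, Grade 3 if 5.0 < x/b ≤ 20. With a normal baseline: Grade 1 if 1 < x ≤ 3, Grade 2 if 3 < x ≤ 5, Grade 3 if 5 < x ≤ 20. From criterion 10f, b ≤ 2.0 at screening. From Appendix 4, the single-value stopping threshold is x ≥ 5.

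**Where the listing starts.** With an abnormal baseline, Grade 2 begins above x = 3b. A value of 5xULN stays at Grade 1 when 5 ≤ 3b, that is b ≥ 5/3 = 1.67. At the entry limit, 3b = 3 × 2.0 = 6.0. The gap for the 5xULN criterion is therefore baseline 1.67 to 2.0xULN with a peak from 5xULN up to 3b, at most 6xULN.

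| Baseline (xULN) | Grade 1 upper limit (xULN) | Grade at 5.0xULN | Grade at 5.5xULN | Grade at 6.0xULN |
|---|---|---|---|---|
| 1.0 (normal) | 3.0 | 2 | 3 | 3 |
| 1.2 | 3.6 | 2 | 2 | 2 |
| 1.5 | 4.5 | 2 | 2 | 2 |
| 1.67 | 5.0 | 1 | 2 | 2 |
| 1.8 | 5.4 | 1 | 2 | 2 |
| 1.9 | 5.7 | 1 | 1 | 2 |
| 2.0 | 6.0 | 1 | 1 | 1 |

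At baseline 2.0, for example, 5.5/2.0 = 2.75, which is Grade 1.

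**The wider band.** For any b > 1, values above 3xULN and up to 3b are below Grade 2, whereas from a normal baseline they are Grade 2 or higher and listed. At b = 1.2, a value of 3.5xULN is 3.5/1.2 = 2.92 times baseline, so Grade 1. Such values are ungraded only if x < 1.5b, which for x above 3 requires b > 2.

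**Baselines above 2xULN.** Criterion 10f applies at screening. The note closing Protocol 5.2 excludes a participant whose available results before first dose no longer qualify, so a baseline above 2xULN needs a Week 0 result not available before dosing. If that happened the gap would widen: baseline 3.0 and peak 8.0 gives 8.0/3.0 = 2.67, still Grade 1.

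**Treatment emergence.** SAP 5.6.3.1 concludes treatment emergence for toxicity grades when the post-baseline value is worse than baseline, without saying whether the grade or the measured value is compared. Under SAP 6.10, a baseline of 2.0xULN is Grade 1 on the ULN scale. A rise to 5.5xULN is Grade 1 on the baseline scale. Compared by grade, this is not treatment emergent; compared by value, it is.

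**Other laboratory outputs.** In the Week 12 shift table this participant is high-to-high, or high-to-normal if the peak has resolved. Under the normal-range rule in SAP 5.6.3.1, a participant already above the upper limit at baseline cannot have a treatment-emergent high value.

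**The case against.** The strongest reply is that the participant is not lost. Protocol 10.4.2 requires anyone meeting a stopping criterion to stop, to be reported to the sponsor within 24 hours, and to have an adverse event form completed. SAP 5.2 lists those who discontinue study intervention and tabulates reasons. SAP 5.6.2 tabulates and lists adverse events leading to discontinuation. SAP 6.8 carries the possible Hy's law definition, though adverse events of special interest are summarized only as needed and an isolated rise to 5xULN is not a Hy's law case. The participant could also enter the laboratory listing through another test. All of this stands. A reader might infer that a liver signal disappears from the report; the documents do not support that. What remains is that those outputs are not specified to show the ULN multiple or the criterion met, and they do not correct the grade table.

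A second reply is that Table 3 is labelled CTCAE version 5.0 and states its abnormal-baseline rule openly, and that a reporting scale may differ from a stopping rule. That also stands: nothing here shows a transcription error. For normal-baseline participants the grades already fall almost on the ULN bands, apart from values exactly at the cut-offs, so it would be too broad to say that no planned output shows ULN multiples.

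Third, the final outputs cannot be fully checked. The Data Presentation Specifications and Master protocol 9.4.4 are not available. The grading rule and listing trigger, however, are set in the SAP itself.

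**Conclusion.** The point holds within limits. Under the SAP's stated rules, a participant with baseline ALT or AST of 1.67 to 2.0xULN and a peak from 5xULN to three times baseline (at most 6xULN) meets a mandatory stopping criterion but is Grade 1 and unlisted for that test. The same mismatch, for values above 3xULN and up to three times baseline, affects every abnormal baseline. If treatment emergence is judged by grade, a rise from 2.0 to 5.5xULN would not count.

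This assumes that baseline stays within the screening limit and that Table 3 is applied as written. The documents do not say how many participants would have a raised baseline, so neither the number affected nor any understatement in the tables can be estimated.

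Two stronger readings should be resisted. One is that a rise from 2.0 to 2.9xULN, which is 1.45 times baseline and so ungraded, is a missed liver signal: no Appendix 4 criterion begins below 3xULN. The other is that the report would show grades falling as ALT rises: no table of shifts in grade is planned.

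**What to change.** Keep CTCAE grading and change three things in SAP 5.6.3.1.

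1. Add a by-arm table of maximum post-baseline ALT and AST at ≥3xULN and ≥5xULN whatever the baseline, plus ALT/AST ≥3xULN with total bilirubin ≥2xULN or INR >1.5 where measured. Show possible Hy's law cases with the further condition of ALP <2xULN, as in Protocol 8.3.7.
2. Change the listing trigger to CTCAE Grade ≥2, or ALT/AST ≥3xULN.
3. State that treatment emergence for ALT and AST is judged on the measured value, not on grades taken from two different scales.

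ALP and bilirubin need no 3xULN or 5xULN bands; Appendix 4 has no such cut-offs for them. INR is not in the routine panel in Protocol Appendix 5, hence the restriction to measured values.

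The cost is one extra table and a slightly longer listing. No new data are needed, and no stopping rule changes.

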### 5.6.3.2. Vital Signs and Physical Examination Findings

Vital signs are measured at every visit. The listing for participants with clinically important results will be provided as appropriate.

Continuous vital sign parameters collected will be summarized at each assessment time point. Descriptive statistics (mean, standard deviation, median, minimum and maximum) will be presented by intervention groups.

### 5.6.3.3. Electrocardiogram

The listing for participants with clinically important results will be provided as appropriate.

## 5.7. Other Analyses

### 5.7.1. Pharmacokinetics

PK analyses will be based on the Pharmacokinetics Analysis Set (Section 4).

#### 5.7.1.1. PTG-200 Concentrations

Blood, colonic tissue and fecal samples for determining PTG-200 concentrations will be collected from all participants according to the schedule in the Protocol Schedule of Activities. Plasma, colonic tissue and fecal PTG-200 concentrations will be used to evaluate local and systemic drug exposure.

Plasma, colonic tissue and fecal PTG-200 concentrations will be summarized using descriptive statistics (i.e., n, arithmetic mean, standard deviation [SD], coefficient of variation [%CV], median, range [minimum and maximum], and interquartile [IQ] range) at each visit. PK data may be displayed graphically.

The following analyses will be performed as appropriate.

- Summary of plasma PTG-200 concentration over time
- Proportion of participants with plasma PTG-200 concentration below the lowest quantifiable concentration in a sample at each visit
- Summary of plasma PTG-200 concentrations over time by baseline body weight (quartiles). Other covariates may also be applied.
- Plots of median plasma PTG-200 concentrations over time

- Plots of median plasma PTG-200 concentrations over time by baseline body weight ( $\leq$ median,  $>$ median).

As applicable, a similar approach as described above for plasma PTG-200 concentration will also be applied to colonic tissue and fecal PTG-200 concentrations.

### 5.7.1.2. Data Handling Rules

Unless otherwise specified, the following data handling rules will apply to PK sample analyses:

- Plasma concentration summaries will be based on the actual treatment received.
- All plasma, colonic tissue and fecal concentration summaries for a particular timepoint will include data obtained from treated participants at the timepoint of interest without imputing any missing data.
- A concentration not quantifiable (below the lower limit of quantification) will be treated as 0 in the summary statistics and shown as the lower limit of quantification ( $<$  LLOQ) in the data listings.
- The data from a participant who meets 1 of the following dosing deviation criteria will be excluded from the by-visit data analyses from that point onwards:
  - Discontinued study agent administrations
  - Skipped an administration
  - Received an incomplete/ incorrect dose
  - Received an incorrect study agent
  - Received an additional dose
  - Received an administration outside the dosing window specified in [Table](#) .

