1.3. Schedule of Activities

A consolidated Schedule of Activities for the Master protocol PLATFORMPACRD2001 and this ISA is presented in [Table 1](#).

Table 1: Consolidated Schedule of Activities - PLATFORMPACRD2001 and 67864238PACRD2001										
67864238PACRD2001 specific events	Period	Screening ^a	Treatment Phase ^b				Early Termination ^c	Final Safety Follow-up ^d		
			Week	-5 weeks	0	2	4	8	12	
Study Procedures										
Screening/Administrative										
Informed consent ^e		X								
Master protocol inclusion/exclusion criteria ^f		X		X						
X JNJ-67864238 inclusion/exclusion criteria ^f		X		X						
Medical history and demographics		X								
Immunization history		X								
Stool studies to evaluate for enteric pathogens ^g				X						
Height		X								
X^v QuantiFERON-TB test		X								
X^w Chest radiograph		X								
HIV, HBV and HCV testing		X								
Follicle stimulating hormone test (optional at the discretion of the investigator)				X						
Serum pregnancy test ^h		X								
X (Week 4 only) 12-lead ECG		X			X		X	X		
Training on diary completion		X								
Randomization				X						
Study Intervention Administration										
X Dispense study intervention				X	X	X	X			
X Administer study intervention				Daily Self-Administration						
X Study intervention accountability				X	X	X	X	X		
Safety Assessments										
Physical examination		X				X	X	X		

Table 1: Consolidated Schedule of Activities - PLATFORMPACRD2001 and 67864238PACRD2001									
67864238PACRD2001 specific events	Period	Screening ^a	Treatment Phase ^b					Early Termination ^c	Final Safety Follow-up ^d
			Week	-5 weeks	0	2	4	8	12
Study Procedures									
Body weight		X		X	X	X	X	X	X
Vital signs ⁱ		X		X	X	X	X	X	X
Urine pregnancy test ^j				X	X	X	X	X	X
Concomitant therapy review		X		X	X	X	X	X	X
Adverse events review		X		X	X	X	X	X	X
X^x Tuberculosis evaluation/other infection assessment		X		X	X	X	X	X	X
Efficacy Assessments									
Collect and review diary entries ^k				X	X	X	X	X	X
X^{bb, cc} CDAI assessments ^{l, m}		X		X	X	X	X	X	X
Fistula exam				X	X	X	X	X	X
Abdominal pain NRS assessment ⁿ				X	X	X	X	X	X
Stool sample (fecal lactoferrin and calprotectin) ^o		X		X	X	X	X	X	X
X^y Video ileocolonoscopy with biopsies for RNA and histology ^p		X						X	X
PROMIS-29 ^q				X				X	X
PGIC								X	X
PGIS				X				X	X
Clinical Laboratory Assessments									
Hematology ^{r, s}		X		X	X	X	X	X	X
Chemistry ^{r, s}		X		X	X	X	X	X	X
CRP		X		X	X	X	X	X	X
Pharmacokinetics/Immunogenicity									

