- g. Stool studies for enteric pathogens may be performed at either the central or a local laboratory and must include a stool culture and Clostridium difficile toxin assay. These must have been performed within 4 months before Week 0. Additional testing, such as ova and parasites or Escherichia coli O157:H7 assessment may be performed at the investigator's clinical discretion.
- h. Must be performed before any administration of the study intervention for female participants of childbearing potential.
- i. Temperature, pulse/heart rate, respiratory rate, and blood pressure.
- j. Must be performed at every visit for female participants of childbearing potential.
- k. For all visits up to and including Week 12, daily diary information should be collected for every day prior to each visit.
- l. Hematocrit value obtained during screening will be used to calculate CDAI at Week 0.
- m. CDAI will calculated using the total number of liquid or very soft stools in the previous 7 days. During the screening visit, participants should be trained on how to complete the CDAI diary, including instructions that only liquid and very loose stools should be scored using the Bristol Stool Form Scale as a reference.
- n. Participant will complete the abdominal pain numeric rating scale (NRS) assessment as a daily diary entry, beginning during screening, and bring the diary to each visit. For all visits up to and including Week 12, daily diary information should be collected for every day prior to the visits. Patient-reported outcome components of the CDAI should be performed first (ie, before the NRS).
- o. Stool samples required for the visits with a video ileocolonoscopy should be obtained before the start of the bowel preparation for the video ileocolonoscopy that is also scheduled for the visit.
- p. Because these procedures must not interfere with the collection of CDAI data, if performed on the day of these visits, the 7 days before the initiation of the colonoscopy preparation should be used to calculate CDAI scores for these visits. If the video ileocolonoscopic examination is not performed on the day of the

visit, it must be performed at least 8 days before the Week 0 visit and no more than 8 days before the Week 12 visit or early termination visit. The Simplified Endoscopic Score for Crohn's disease (SES-CD) will be calculated by the central reader.

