8.5.1. Evaluations

Venous blood samples and fecal samples will be collected for the determination of plasma and fecal concentrations of JNJ-67864238 according to the Schedule of Activities ([Table 1](#)).

Blood samples for the measurement of JNJ-67864238 plasma concentrations will be collected from all randomized participants as follows:

- Before study intervention administration at Week 0, Week 2, Week 4, Week 8, and Week 12
- After study intervention administration at Week 12 within 2 to 4 hours
- The early termination visit (if applicable)

The exact dates and times of PK blood sampling must be recorded on the laboratory requisition form. Additional information about the collection, handling, and shipment of biological samples can be found in the applicable Laboratory Manual.

Stool samples for the measurement of JNJ-67864238 concentrations will be collected from all randomized participants as follows:

- At Week 2, Week 4, Week 8, and Week 12
- The early termination visit (if applicable)

Biopsy samples collected during video ileocolonoscopy will be used for the measurement of JNJ-67864238 tissue concentration.

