9.4.5. Other Analyses

Refer to Section 9.4.5 of the Master protocol PLATFORMPACRD2001 for additional information for other analyses.

Pharmacokinetic Analyses

Data will be listed for all participants with available plasma, fecal, and biopsy tissue concentrations per treatment arm. Participants will be excluded from the descriptive statistics if their data do not allow for accurate assessment of the concentration data (eg, incomplete administration of the study intervention; missing information of dosing and sampling times).

All concentrations below the lowest quantifiable concentration or missing data will be labeled as such in the concentration database. All participants and samples excluded from the analysis will be clearly documented in the study report.

For each treatment arm, descriptive statistics, including arithmetic mean, standard deviation, coefficient of variation, median, minimum, and maximum will be calculated.

Biomarkers Analyses

Refer to Section 9.4.5 of the Master protocol PLATFORMPACRD2001 for biomarker analyses.

Immunogenicity Analyses

The incidence of anti-JNJ-67864238 antibodies will be summarized for all participants who receive at least 1 dose of JNJ-67864238 and have appropriate samples for detection of antibodies to JNJ-67864238 (ie, participants with at least 1 sample obtained after their first dose of JNJ-67864238). Antibodies may be summarized as induced or pre-existing if a predose sample at Week 0 is obtained.

A listing of participants who are positive for antibodies to JNJ-67864238 will be provided. The maximum titers of antibodies to JNJ-67864238 will be summarized for participants who are positive for antibodies to JNJ-67864238.

Systemic JNJ-67864238 concentrations and clinical efficacy/safety endpoints may be summarized by antibody to JNJ-67864238 status if sufficient numbers of participants are positive for antibodies. Other immunogenicity analyses may be performed to further characterize the immune responses that are generated.

Pharmacodynamic and Disease-specific Analyses

Planned biomarker analyses may be deferred if emerging study data show no likelihood of providing useful scientific information. Any PD samples received by the contract vendor or sponsor after the cutoff date will not be analyzed, and therefore, excluded from the PD analysis.

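### Read literally, SAP 5.7.1.2 drops a participant from all later by-visit PK summaries after one dosing deviation, however far it was from the sample (minor)

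*SAP*

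**What the plan says.** SAP Section 5.7.1.2 sets the data handling rules for PK samples. The data of a participant "who meets 1 of the following dosing deviation criteria will be excluded from the by-visit data analyses from that point onwards". There are six criteria. Besides discontinuation, a wrong study agent and dosing outside the Table 4 window, they include "Skipped an administration", an incomplete or incorrect dose, and an additional dose. The SAP sets no minimum number of deviations, no look-back before a sample and no re-entry. Table 4 gives windows of 5 days either side of scheduled visit days through Week 12, and 14 days for follow-up visits.

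The summaries affected are those of plasma, colonic tissue and stool concentrations, which "will be used to evaluate local and systemic drug exposure" (SAP Section 5.7.1.1).

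Protocol Table 1 gives the dosing pattern as "Daily Self-Administration"; the exact frequency is redacted. Plasma is drawn "Before study intervention administration at Week 0, Week 2, Week 4, Week 8, and Week 12" (Protocol Section 8.5.1), with a post-dose sample at Week 12. Stool is sampled at Weeks 2, 4, 8 and 12. The on-treatment biopsy is at Week 12 or early termination.

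Protocol Section 9.4.5 has its own exclusion: "Participants will be excluded from the descriptive statistics if their data do not allow for accurate assessment of the concentration data". Its examples are incomplete administration and "missing information of dosing and sampling times".

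**The concern.** The rule works on the participant and never lapses. A tablet missed in Week 1 removes that person from the Week 2, 4, 8 and 12 summaries, even if every later dose was taken. With months of home dosing, some deviation is to be expected in an otherwise adherent participant. Followed literally, the Week 12 summary describes only people with no recorded deviation since Day 1, rather than the treated arm.

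Protocol Section 9.4.5 asks whether the concentration can be accurately assessed. The SAP rule omits that question, so it can remove samples that would pass it.

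Because Protocol Section 8.5.3 says PK parameters cannot be estimated, the by-visit concentrations are the main planned description of exposure for a drug meant to act in the gut. The optional PK-efficacy work in SAP Section 5.7.1.3 may inherit the same restriction.

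**Working it through.** The plan gives no expected retention figure, so there is nothing to reproduce. The check asks how many PK visits one deviation costs.

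**Inputs.** Dose days 1 to 84 (12 weeks, at least one dose a day). Nominal sample days 15, 29, 57 and 85 (SAP Table 1, Weeks 2, 4, 8 and 12). Planned active arm 54. Dropout, missing samples and early-termination samples are ignored.

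**1. Current rule, literal reading.** A missed dose costs every later visit:

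| Day missed | Number of days | Visits lost |
|---|---|---|
| 1–14 | 14 | 4 |
| 15–28 | 14 | 3 |
| 29–56 | 28 | 2 |
| 57–84 | 28 | 1 |

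Mean over a random day: (14×4 + 14×3 + 28×2 + 28×1)/84 = 182/84 = 2.17 of 4 visits. No adherence assumption is needed.

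**2. Sample-level rule with an L-day look-back (L is illustrative).** A missed dose costs a visit only if it falls within L days before a sample, so the mean is 4L/84:
- L = 1: 4/84 = 0.05
- L = 3: 12/84 = 0.14
- L = 7: 28/84 = 0.33

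With L = 7, 84 − 28 = 56 of the 84 dose days (67%) lie too far before the next sample to matter.

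**3. Narrow reading: only doses on nominal visit days count.** Doses on Days 1, 15, 29 and 57 then cost 4, 3, 2 and 1 later visits, and all other days cost none: (4 + 3 + 2 + 1)/84 = 10/84 = 0.12. This reading would ignore a dose skipped the day before a pre-dose sample, so it is not a satisfactory rule either.

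**4. Why no retained number is given for Week 12.** Take an assumed adherence of 99% under the literal rule:
- once daily, independent misses: 54 × 0.99^84 = 23.2
- twice daily, independent misses: 54 × 0.99^168 = 10.0
- once daily, misses concentrated in some participants (beta-binomial, correlation 0.5, a = 0.99, b = 0.01): 54 × B(a+84, b)/B(a, b) = 51.4

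One assumed adherence gives anything from about 10 to 51 of 54. Adherence and clustering are not in the documents and frequency is redacted, so these figures show only that the number is undetermined.

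**5. Table 4.** If its window applied to every dose, Day 7 would be the first day more than 5 days from any scheduled visit (Day 1 + 5 = Day 6; Day 15 − 5 = Day 10). Every adherent participant would then be excluded from Day 7. That cannot be intended, so it is a gap in wording only.

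**The case against.** The strongest objection is that the list was written for visit-based dosing. Table 4 ties administrations to scheduled visits and even has a window for follow-up visits, when no study drug is given. If an administration means a visit-day dose throughout the list, step 3 applies and most of the loss disappears. This stands as a plausible reading. It does not remove the point, because the SAP nowhere limits skipped doses to visit days, and Protocol Section 6.1 requires dose dates and times to be recorded.

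A reader might infer that the SAP contradicts the protocol. It does not clearly do so. Protocol Section 9.4.5 also excludes participants rather than samples and names incomplete administration. The difference is the missing condition on accurate assessment.

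A reader might also infer that valid data are thrown away. The support for validity is limited to plasma: the Phase 1 summary in Protocol Section 2.2 compares Day 1 with Day 14 in healthy men and finds no sign of accumulation, up to a redacted dose level. This trial uses the highest Phase 1 dosage (Section 4.3), which that statement is not shown to cover. Nothing comparable is given for stool or tissue. The concentrations also remain in the listings (Protocol Section 9.4.5), and exclusions are to be documented in the study report (SAP Section 5.7.1.2), so summaries could be rerun.

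Finally, a sample-level rule that automatically excluded undocumented dosing could remove more samples than the present rule. That objection is sound and shapes the fix.

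**Conclusion.** The point holds as a minor one, on the literal wording. A single deviation permanently removes a participant from the by-visit PK summaries without asking whether the later sample can be assessed. One missed dose on a random day then costs on average 2.17 of 4 post-baseline plasma and stool visits, against 0.33 with a 7-day look-back. Both figures rest on nominal visit days and on every dose counting. If only visit-day doses count, the loss is much smaller.

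It would be tempting to conclude that few participants would remain at Week 12, or that the summaries would be biased in a known direction. The documents support neither: they do not give the inputs for a retained number, and nothing shows how concentrations differ between participants with and without deviations. No range of gain from changing the rule should be claimed.

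The effect is confined to descriptive PK summaries and optional PK-efficacy work. The primary endpoint, the other efficacy analyses and the CDAI and SES-CD decision rules are untouched.

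**What to change.** Before unblinding, amend SAP Section 5.7.1.2 as follows.

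- Exclude a concentration, not a participant. Exclude it only if a recorded dosing deviation falls within a pre-specified look-back before that sample, or if the sample follows permanent discontinuation. Keep later samples from the same participant.
- Have the PK team set and justify the look-back separately for plasma, stool and tissue. The documents supply none; the 7 days above is only an illustration.
- Count the look-back from the actual sample date. A biopsy not done on the visit day may be taken "no more than 8 days before the Week 12 visit or early termination visit".
- Flag samples whose look-back dosing is undocumented and judge them under Protocol Section 9.4.5, rather than excluding them automatically.
- State that Table 4 governs visit or sample timing only, or delete it.
- Report the number of samples excluded by reason and visit.

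The cost is low: a wording change and somewhat more data handling. The rule will rely on home dosing records, which may be incomplete: Protocol Section 6.4 has the site assess compliance at clinic visits, and Section 9.4.5 itself expects some missing dosing times. A look-back must also be defended for each matrix.
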